4.4 PARTICIPANT MANAGEMENT

4.4.1 PARTICIPANT RESPONSIBILITIES

In addition to meeting the eligibility criteria listed above, participants will also be asked to agree to not participate in any other research study or donate blood during their participation in the RV 460 study.

4.4.2 WITHDRAWAL FROM THE STUDY, DISCONTINUATION OF STUDY PRODUCT, OR STUDY TERMINATION

4.4.2.1 Withdrawal

- Repeated failure to comply with protocol requirements
- Recommended withdrawal by the study investigator, e.g., because of worsening health status, intercurrent illness, or AEs interfering with study assessments as determined by the site investigator
- Participant requests withdrawal

Each participant has the right to withdraw from the study at any time for any reason without affecting the right to treatment. The study staff should attempt to contact participants who did not return for scheduled visits or follow-up. Although the participant is not obliged to give a reason for withdrawing prematurely, the investigator should make a reasonable effort to ascertain the reason(s) while fully respecting the participant's rights. Participants who elect to not receive additional vaccinations may be asked to continue follow up assessment for safety until resolution in the case of an on-going AE.

The study team will use several approaches that include at least three phone call attempts each to participant and to a confidant through contacts the participant would have provided and documented in the participant contact information form. If the participant is not located by phone call attempts, a home visit will be done to locate the participant. If after the home visit the participant cannot be contacted, they will be declared lost to follow-up.

For those participants who are unable to continue participation in the study, but who do not withdraw consent, an exit visit will be conducted. Any participant who withdraws consent will not have any further data collected after consent has been withdrawn.

Participants may elect to withdraw consent for future use of their biological specimens or data at any time. This will be recorded in the EDC and source and the data samples will be marked to not be used in the future. The data and specimens will be destroyed within one year of receiving notification from the protocol chair that all protocol testing is complete. Samples remaining in the KEMRI/USAMDR-A CRC repository will be destroyed by laboratory staff following approved laboratory procedures.

See Appendix A: Schedule of Evaluations

4.4.2.2 Participant Replacement

Participants who withdraw, are withdrawn from this study, or are lost to follow-up after signing the informed consent form (ICF) and administration of the study product will only be replaced if enrollment is still open. If a participant withdraws from the study or discontinues vaccination before all slots have been filled, the vacated randomization slot will be filled with the next available participant.

4.4.2.3 Early Discontinuation of Vaccinations or Withdrawal of a Study Participant

A participant may have vaccinations discontinued or will be taken out of the study entirely under the following circumstances:

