4.4.2.3.1 Immediate Early Discontinuation

1. Upon learning of pregnancy
2. Due to an SAE that is believed to be related to study vaccination, including
 - a. Any Grade 3 systemic adverse reaction that is assessed as related to the study agent,
 - b. Any Grade 4 adverse event assessed as related to the study agent, and
3. Infection with HIV-1.

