4.4.3 MANAGEMENT OF MEDICAL CONDITIONS

Participants will be offered pre-test counseling before HIV testing is done. When giving HIV results to participants, post-test counseling will be done, and those who test positive will be referred to KCRH, or any other health facility of their choice, for HIV care and treatment. The HIV pre and post-testing counselling will be provided by a psychological counsellor at the site, as well as by study clinicians/nurses trained in HIV counselling and testing.

All individuals with clinical sexually transmitted infections (STIs) will be treated according to the Kenya Ministry of Health local standards of care.

For all other medical illnesses and abnormal laboratory values, participants will consult study staff for treatment and or referral to the appropriate health facility during the study period.

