4.4.4 MANAGEMENT OF PARTICIPANTS WHO BECOME PREGNANT

Pregnant women are excluded from enrollment, however, if a participant becomes pregnant during the study, further vaccinations will be stopped, and she will be referred for maternal and child health services. Participants will continue to be followed for the remainder of the study period for safety, and the study team will follow the course of the pregnancy until the outcome is documented. During subsequent study visits, blood draws will be conducted for safety evaluations only. No optional collections or procedures will be performed.

The Kericho site PI or designated associate investigator will be responsible for reporting any pregnancy to the PSRT and the study database. The PSRT will review this information. The site PI will forward notification as necessary to the WRAIR IRB and KEMRI SERU (Scientific and Ethics Review Unit).

Pregnancy outcomes will be recorded via a standardized case report form. Information documented on this form will include the date of last menstrual period, the date that the pregnancy was confirmed, any history of complications during prior pregnancies (such as congenital abnormalities or spontaneous abortions), and the outcome of the pregnancy including date of termination or delivery, any complications of pregnancy, and the status of the child. A separate case report form will be completed for the delivered child to document date of delivery, gender, weight, the presence of any congenital abnormalities, American Pediatric Gross Assessment Record (APGAR) score, HIV status, and any other complication of delivery.

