8.1.8.4 Type and Duration of Follow-up of Participants after Adverse Events

AEs will be assessed and followed from initial recognition of the AE through end of the protocol defined follow-up period. SAEs will be followed up through resolution even if duration of follow-up goes beyond the protocol-defined the follow-up period. Resolution of an AE is defined as the return to pre-treatment status or stabilization of the condition with the expectation that it will remain chronic.

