9 HUMAN SUBJECTS PROTECTION

9.1 INFORMED CONSENT

The legal age at which individuals can provide their own consent to participate in research is 18 years. Consent forms will be available in English and Kiswahili.

There are four consent forms to be used for this study:

1. Main Informed Consent Form
2. Optional Procedures Consent Form
3. Withdrawal of Consent Form (as needed)
4. Photography Consent Form (as needed)

Information will be given in both oral and written form whenever possible and deemed appropriate by the IRB. A clinical investigator or designee will describe the study to potential participants. The investigator or designee (e.g., study coordinator) shall give the participant ample opportunity to inquire about details of the study, discuss with other people and ask any questions before dating and signing the consent forms. Participant information and consent form language will be at a reading level to be fully comprehensible to the prospective participants.

The participant and the study staff conducting the informed consent explanation will sign and date the consent form. The participant's signature confirms that she or he has understood the information. Each participant's consent form will be kept in his or her study file and a copy will be given to the participant to take home on the same day. Any amendments to the protocol resulting in a change in study procedures will necessitate that the study participants be informed, and additional informed consent obtained if necessary.

In accordance with 32 CFR 219, 45 CFR 46 and 21 CFR 50 and Good Clinical Practice, the participant may terminate participation in the study at any time for any reason without penalty. Additionally, if the participant is unable or unwilling to adhere to the protocol design, the investigator may terminate their participation. Under such circumstances, data and sample already collected may be stored and available for analysis. In addition, if the administration of research product has occurred, following for safety will be attempted.

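### Section 4.4.2.3 allows removal from the study after a related severe reaction or HIV-1 infection, and only pregnancy has a rule that keeps the participant under safety follow-up to study end

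*Protocol*

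**What the plan says.** Section 4.4.2.3 opens with "A participant may have vaccinations discontinued or will be taken out of the study entirely under the following circumstances". The list beneath it, in 4.4.2.3.1 (Immediate Early Discontinuation), has three triggers: pregnancy, an SAE believed related to vaccination, and HIV-1 infection. The SAE item is expanded to include "Any Grade 3 systemic adverse reaction that is assessed as related to the study agent" and any related Grade 4 event.

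For pregnancy, Section 4.4.4, repeated in 10.2.2, stops vaccination and adds: "Participants will continue to be followed for the remainder of the study period for safety".

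Other provisions that bear on follow-up are:

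- Section 4.4.2.1: participants who elect to stop dosing "may be asked to continue follow up assessment for safety until resolution in the case of an on-going AE"; for those "who are unable to continue participation in the study, but who do not withdraw consent, an exit visit will be conducted".
- Section 4.4.3, on HIV testing: "those who test positive will be referred to KCRH, or any other health facility of their choice, for HIV care and treatment".
- Section 8.1.8.4: "SAEs will be followed up through resolution", beyond the follow-up period if necessary. Sections 8.1.3, 8.1.4 and 8.2.1.4 likewise follow AEs and SAEs to resolution or stability.
- Section 9.1: if participation is terminated by the participant, or by the investigator for non-adherence, and product has been given, "following for safety will be attempted".
- Section 8.1.6 and Appendix A note 9: medically attended adverse events (MAAEs) are followed for 12 months after the last vaccination.
- Section 8.2.1.3: the expedited reporting period ends when a participant is discontinued from study activity for any reason. Section 8.2.1.1 makes potentially immune-mediated conditions (PIMMCs) expedited events.

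**The concern.** Stopping the product and leaving the study are different actions with different consequences for the data. Section 4.4.2.3 offers both for the same triggers and gives no basis for choosing.

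Safety is the primary endpoint. Section 8.1.6 ties the 12-month MAAE period to a theoretical risk of autoimmune or auto-inflammatory disease with adjuvants such as ALF43 and dmLT. Participants who had a related severe reaction are those in whom later events would be of most interest, yet the text lets them be removed. Late surveillance would then be thinned selectively among reactors, and no analysis could recover data that were not collected. For HIV-1 infection, Section 9.2.1.4 says it is unknown whether the vaccines alter the course of disease, so removal would end study observation where that question arises.

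**Working it through.** **1. What each trigger secures if the participant is removed**

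| Trigger | Follow-up of the triggering event | Follow-up of the person for new or late events |
|---|---|---|
| Pregnancy | To outcome (4.4.4, 10.2.2) | Secured to study end (4.4.4, 10.2.2) |
| Related SAE, related Grade 3 systemic or related Grade 4 event | To resolution or stability (8.1.3, 8.1.4, 8.1.8.4, 8.2.1.4) | Not secured |
| HIV-1 infection | Referral to care (4.4.3) | Not secured |

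The general provisions do not fill the last column. The exit visit in 4.4.2.1 is a single contact. The clause for those who decline further doses is optional and tied to an on-going AE. Section 9.1 promises an attempt and is written for participants who leave or do not adhere.

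**2. Loss per removed participant**

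The benchmark is the protocol's own: 12 months, about 52 weeks, after the last dose. A participant removed straight after any dose loses at most about 52 weeks of that surveillance, whichever dose it was.

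Doses are scheduled at weeks 0, 4, 12, 20, 32 and 56. Adding 52 gives weeks 52, 56, 64, 72, 84 and 108. All fall at or before week 108, when the final telephone contacts end, so the existing schedule already covers the period.

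**3. Precision**

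For zero events in n participants, the exact two-sided 95% upper limit is 1 − 0.025^(1/n). The protocol's Table 5 gives 21.8% for n = 15 and 4.8% for the 75 ALF43 recipients, and the formula reproduces both. The number removed is not known; 1 or 2 is an assumption, with nothing contributed to the late period.

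| Set | None lost | 1 lost | 2 lost |
|---|---|---|---|
| One vaccine group | n = 15: 21.80% | n = 14: 23.16% | n = 13: 24.71% |
| Any ALF43 | n = 75: 4.80% | n = 74: 4.86% | n = 73: 4.93% |

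The limit rises by at most 2.9 percentage points (24.71 − 21.80) in a single group and by 0.13 points (4.93 − 4.80) across ALF43 recipients. What matters is which participants are lost rather than the width of the interval.

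**The case against.** The best defence is that the section is meant to stop product only. The heading of 4.4.2 separates withdrawal from the study from discontinuation of study product. Investigator-recommended withdrawal has its own list in 4.4.2.1. The triggers sit under a subheading about discontinuation, and pregnancy, the first of them, is resolved as stopping vaccination. Section 7.2.2 says SAEs, AEs and PIMMCs are recorded to the end of the trial, and Appendix A note 9 makes no exception for people off vaccine. Section 6.1.3 plans viral sequencing in infected volunteers. A related SAE also pauses the trial and goes to the safety review team (8.3.1), so the site does not handle it alone. This is good evidence of intent. It does not override a governing sentence and a section title that both name removal or withdrawal. Nor would one non-serious related Grade 3 or 4 event, or an HIV infection, trigger that pause.

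Three stronger readings are tempting, and the document does not support them:

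- A reader might infer that only pregnancy carries any later safety follow-up. In fact the triggering SAE or AE is followed to resolution or stability under several sections; what is missing is follow-up of the person.
- A reader might count the loss to week 108, giving up to 108 weeks after dose 1. Against the 12-month benchmark it is about 52 weeks, and even that assumes no attempted follow-up succeeds.
- A reader might infer that reactors must be removed or that their reactions go uncounted. Removal is one of two permitted outcomes, and the triggering event is already recorded.

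**Conclusion.** The concern holds in this limited form. The protocol permits, for related severe events and HIV-1 infection, a removal that its own pregnancy rule rules out, and no other section guarantees continued surveillance of those removed. The loss is at most about 52 weeks per person, selective among reactors for the related-event triggers, with little effect on confidence limits. This assumes that a site uses the removal option and that attempted follow-up yields nothing; how often either would happen cannot be judged from the protocol. The consent forms and the manual of operations were not available and might narrow the gap. It is worth correcting because the stated rule works against the stated surveillance period, but it does not threaten the analysis of the triggering events.

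**What to change.** In 4.4.2.3, state that these triggers stop vaccination only. SAE, MAAE and PIMMC follow-up then continues on the existing visits and calls to study end, and for at least 12 months after the last dose received, unless consent is withdrawn. Limit blood draws to safety samples unless otherwise agreed, as the pregnancy rule does. In 4.4.2.1, state that the exit visit does not replace this follow-up. Participants followed in this way remain in study activity, so 8.2.1.3 needs only a cross-reference.

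The cost is a wording amendment with the usual ethics and regulatory approvals (10.4), and continued visits for a few participants on a schedule that already exists.

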4.4.2.3.1 Immediate Early Discontinuation

1. Upon learning of pregnancy
2. Due to an SAE that is believed to be related to study vaccination, including
 - a. Any Grade 3 systemic adverse reaction that is assessed as related to the study agent,
 - b. Any Grade 4 adverse event assessed as related to the study agent, and
3. Infection with HIV-1.

4.4.3 MANAGEMENT OF MEDICAL CONDITIONS

Participants will be offered pre-test counseling before HIV testing is done. When giving HIV results to participants, post-test counseling will be done, and those who test positive will be referred to KCRH, or any other health facility of their choice, for HIV care and treatment. The HIV pre and post-testing counselling will be provided by a psychological counsellor at the site, as well as by study clinicians/nurses trained in HIV counselling and testing.

All individuals with clinical sexually transmitted infections (STIs) will be treated according to the Kenya Ministry of Health local standards of care.

For all other medical illnesses and abnormal laboratory values, participants will consult study staff for treatment and or referral to the appropriate health facility during the study period.

4.4.4 MANAGEMENT OF PARTICIPANTS WHO BECOME PREGNANT

Pregnant women are excluded from enrollment, however, if a participant becomes pregnant during the study, further vaccinations will be stopped, and she will be referred for maternal and child health services. Participants will continue to be followed for the remainder of the study period for safety, and the study team will follow the course of the pregnancy until the outcome is documented. During subsequent study visits, blood draws will be conducted for safety evaluations only. No optional collections or procedures will be performed.

The Kericho site PI or designated associate investigator will be responsible for reporting any pregnancy to the PSRT and the study database. The PSRT will review this information. The site PI will forward notification as necessary to the WRAIR IRB and KEMRI SERU (Scientific and Ethics Review Unit).

Pregnancy outcomes will be recorded via a standardized case report form. Information documented on this form will include the date of last menstrual period, the date that the pregnancy was confirmed, any history of complications during prior pregnancies (such as congenital abnormalities or spontaneous abortions), and the outcome of the pregnancy including date of termination or delivery, any complications of pregnancy, and the status of the child. A separate case report form will be completed for the delivered child to document date of delivery, gender, weight, the presence of any congenital abnormalities, American Pediatric Gross Assessment Record (APGAR) score, HIV status, and any other complication of delivery.

4.4.5 MANAGEMENT OF PARTICIPANTS WHO BECOME INCARCERATED

Participation of prisoners is not planned, and any participant will be suspended from study visits while incarcerated, except visits or telephone contact for ensuring their safety. No study product will be administered to a participant who is incarcerated. The IRB will be notified of the period of incarceration. Data and samples that were collected before the period of incarceration may still be stored and used for analyses. After release from incarceration, either the participant may return to participation in study visits according to the SOE or study participation may be terminated at the discretion of the PI.

Any participant who is incarcerated will be re-consented before rejoining the study.

4.4.6 MANAGEMENT OF PARTICIPANTS WITH VACCINE-INDUCED SEROPOSITIVITY (VISP) OR SEROREACTIVITY (VISR)

Participants who receive study vaccine (not placebo) may subsequently receive a false positive on an HIV antibody test. Participants are asked to contact the PI or study staff if at any time during or after study participation if an HIV test is requested outside of the study. If a participant has an issue due to a false-positive HIV test result from receiving the vaccination, the PI will provide an explanatory letter, and the study will provide re-testing.

4.4.7 TRANSPORTATION

The study team anticipates that nearly all participants or their confidants will have a phone. For those participants who are unable to be contacted by phone, community mobilizers will contact them with a home visit. In order to adequately locate participant's home, all participants will be dropped home after the first vaccination visit and the exact location of their homes documented in

the locator form. We will use alternative contacts to trace them if they are not home. Study participants will use public transport to and from the study site. Public transportation is good and reliable at recruitment catchment area. Transportation will not be provided by the study team except in the event of extenuating circumstances when a participant does not have adequate means of transportation for clinic visits. If the participant did not use the site's transport, they would also receive reimbursements for transportation, taking into consideration the average cost of travel to the clinic.

4.4.8 UNBLINDING PROCEDURES

Once all study visits have completed, the Kericho site investigators will contact study participants by phone or through a home visit to invite them to come back to the clinic to find out whether they received the study product or placebo. When the participant returns to the clinic for unblinding, they will be given a letter that indicates their study arm.

5 STUDY PROCEDURES

5.1 RECRUITMENT

Potential subjects will be made aware of the need for study participants through planned community sessions, church gatherings, public meetings, government administrative meetings (chief's *baraza*'s) or because of previous trial participation. Participants will be invited to attend a general information session at the KEMRI/USAMRD-A Clinical Research Center. After the information session, individuals that indicate interest in the study will be invited and scheduled to attend a briefing session (using the WARIR IRB approved slides) at their convenience. The Principal Investigator (PI) or designee will conduct briefing sessions at regular intervals throughout the recruitment phase. After the briefing, the potential participants will have the opportunity for questions. All participants interested in this study will subsequently be administered informed consent individually.

5.2 CONSENT PROCEDURES AND SCREENING

All participants that present for screening will be documented in a screening log.

Potential subjects must be literate to participate in the study and the consent forms will be offered in English and Kiswahili. The PI or their designee will review the consent form in detail with potential participants and answer any questions. Written informed consent will be obtained from each participant before any study procedures are performed. All informed consent forms will be administered individually, in a private setting, with respect for confidentiality. Participants will be given ample time and opportunity to inquire about the details of the study, discuss the study with family members or friends, and ask any questions before signing the informed consent forms. A copy of the signed informed consent form will be given to the participant along with a copy of the participant event schedule. The consenting process will be documented in the case report forms (CRFs). After providing signed informed consent, the participant will complete a TOU. Participants can take the TOU three times but must have a passing score of 90% or greater by the third attempt to participate in the study. If after three attempts to pass the TOU, and the participant is unable to do so, the participant will become ineligible for study participation.

Participants who have passed the TOU and have given written informed consent will then undergo a review of complete medical history including medications, physical examination, and screening laboratory assessments to determine eligibility for trial participation.

Counseling on the potential risks of becoming pregnant during this trial will be provided. Pre-HIV test counseling and post-HIV test counseling as well as HIV prevention guidance will be provided during the screening process.

Study participants might be scheduled for a second screening visit to evaluate abnormal, not medically significant, findings (including laboratory tests). If the participant presents with an abnormality or illness that is determined to likely be related to a transient illness, they could also be invited back for reassessment.

Upon screening or rescreening, the investigator may discover an illness or condition that requires treatment. The site will provide primary care and treatment as per Kenyan National guidelines and refer these participants to an appropriate healthcare facility for further evaluation and treatment.

Participants that elect to have cervicovaginal secretion collection will undergo a routine PAP smear for assessment of inflammation or other abnormality including cellular changes. Abnormal results will be discussed with the participant and treatment or referral for care will be provided. Abnormal PAP results are exclusionary for the optional cervicovaginal secretion collection only.

